3.5.3. Other Standard Safety other than AEs

Individual participants' vital signs meeting the criteria outlined in Table 6 of special clinical concern, which align with the Pfizer standard criteria, will be summarized by randomized arm, as part of standard safety-related outputs.

Table 6. Vital Signs to be Monitored

Parameter	Flag Level*	Conventional Units
Systolic Blood Pressure (seated)	< 90	mm Hg
	≥ 30 change from baseline	mm Hg
Diastolic Blood Pressure (seated)	< 50	mm Hg
	≥ 20 change from baseline	mm Hg
Pulse rate (seated)	< 40	Beats per minute (bpm)
	> 120	bpm

^{*}All flag level changes are cumulative from baseline (defined as result closest prior to dosing at Visit 5 (Day 1)

In addition, Pfizer standard criteria for reporting of cardiac conduction intervals will be summarized by randomized arm.

Individual participants' ECGs meeting the criteria outlined in Table 7, which align with the Pfizer standard criteria, will be summarized by randomized arm, as part of standard safety-related outputs.

Table 7. ECG Categories

Parameter	Flag Level*
Maximum Post-dose Corrected QT (Fridericia	≤ 450
method) (QTcF) (msec)	450 - ≤480
	480 - ≤500
	> 500
Maximum Increase from Baseline in QTcF (msec)	≤30
	30 - ≤60
	> 60
Maximum Post-dose PR (msec)	≥300
Maximum Increase from Baseline in PR (msec)	Baseline >200 and max ≥25% increase
	Baseline ≤200 and max ≥50% increase
Maximum Post-dose QRS (msec)	≥140
Maximum Increase from Baseline in QRS (msec)	≥50% increase
Heart Rate (bpm)	<40
	>120

^{*}All flag level changes are cumulative from baseline (defined as result closest prior to dosing at Visit 5 (Day

QTcF (in msec) = $[QT (in \underline{msec})/[cube root of RR interval (in sec)] with RR (in sec) = RR (in msec) x 1000$

[⇒] QTcF -derived by programming as follows -

In addition, changes in background medications (i.e. final Total Daily Dose (TDD) in the study, i.e. End of Treatment, compared to Baseline (pre-Day 1) TDD) for agents used for glycemic control, lipid control, or blood pressure, and *selected* other specific background medications will be summarized as follows:

- Dose increase and decrease in concomitant medication for glycemic control, i.e. medications for
 - Type 1 and 2 Diabetes
 - Metformin dose categories will also be summarized by visit and treatment group
 - The relevant data can be obtained from the CM001_1 page (Anti-diabetic agents category) from the eCRF.
- Dose increase and separately decrease in concomitant lipid-modifying medications, i.e. medications for
 - HDL-C decreased
 - LDL-C increased
 - Triglycerides increased
 - The relevant data can be obtained from the CM001_2, 3 and 5 pages (Hypercholesterolemia category) from the eCRF.
- Dose increase and separately decrease in concomitant blood pressure management medications, i.e. medications for
 - Hypertension
 - The relevant data can be obtained from the CM001_4 pages (Anti-hypertension agents category) from the eCRF.
- Dose increase and separately decrease in concomitant therapies relating to:
 - Hypothyroidism
 - The relevant data can be obtained from the CM001_6 pages (Hypothyroidism medications category) from the eCRF.

To assess for changes in alcohol consumption during the study, changes from baseline in the Alcohol use disorders identification test (AUDIT) questionnaire total score and the Absolute Value in Percent carbohydrate deficient transferrin relative to total transferrin (%CDT), will also be summarized descriptively over time.

Drug-Induced Liver Injury (DILI) and Hy's Law Criteria

A summary table will categorize the number and percentage of participants in each treatment group who meet the criteria, defined differently for participants with Normal baseline

and Abnormal baseline (see Appendix 6 of protocol for definition of potential Hy's Law and Potential DILI)

Participants meeting the AST/ALT and TBili criteria will be categorized as potential Hy's Law cases, and participants who meet the AST/ALT criteria but not the TBili criteria will be categorized as potential DILI cases.

eDish plots will be produced (Peak ALT vs Peak TBili and Peak AST vs Peak TBili), with sectors delineated by the following lines to indicate elevations in ALT, AST and TBili:

- two vertical lines at the point at which Peak ALT (or AST) = 3 x ULN and at 8 x ULN
- a horizontal line at the point at which Peak Total Bilirubin = 1 x ULN and at 2 x ULN

Separate plots will be produced for each treatment group, with males and females identified using different symbols.

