8.2.3. Electrocardiograms

Standard 12-lead ECGs utilizing limb leads (with a 10 second rhythm strip) should be collected at times specified in the SoA-Table A1 using an ECG machine that automatically calculates the heart rate and measures PR, QT, and QTc intervals and QRS complex. Alternative lead placement methodology using torso leads (eg, Mason-Likar) is not recommended given the potential risk of discrepancies with ECGs acquired using standard limb lead placement.

- All scheduled 12-lead ECGs should be performed after the participant has rested quietly for ≥10-minutes in a supine position;
- ECG values of potential clinical concern are listed in Appendix 7.
 - Starting at Visit 4/Baseline, if a machine-read QTc value is prolonged, as defined in Appendix 7, repeat measurements may not be necessary if a qualified physician's interpretation determines that the QTc values are in the acceptable range;
 - Assessment of whether prolonged QTc interval meets criteria as defined in Appendix 7, must assess QTc interval using only the Fridericia's correction (ie, QTcF) either as reported by the 12-lead ECG machine or QTcF derived using sponsor-provided tool and reported QT and RR intervals.
- In some cases, it may be appropriate to repeat abnormal 12-lead ECGs to rule out improper lead placement as contributing to the ECG abnormality; as much as practically, possible, it is important that leads be placed in the same positions each time in order to achieve precise ECG recordings.

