9.4.6.2. Electrocardiogram Analyses

Changes from baseline for the ECG parameters QT interval, heart rate, QTcF interval, PR interval, and QRS interval will be summarized by treatment and time. For purposes of reporting study-level results, QTcF interval will be derived using Fridericia's heart rate correction formula applied to databased QT interval, and RR interval. The number (%) of participants with maximum increases from baseline will be tabulated by treatment as defined in the SAP. Numbers and percentages of participants meeting the categorical criteria summarized in Table 5 will be provided and individual values listed in the study report. No formal inferential statistics will be applied to the ECG data.

Table 5. Safety-Related Assessment of QT and QTcF Interval

Degree of Prolongation	QTcF Interval Prolongation (msec)			Uncorrected QT
	Mild (msec)	Mild (msec) Moderate		Interval (msec)
		(msec)		
Absolute value	>450-480	>480-500	>500	> 500
Increase from baseline		30-60	>60	

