10.7. Appendix 7: ECG Findings of Potential Clinical Concern

ECG Findings That May Qualify as Adverse Events

- Marked sinus bradycardia (rate <40 bpm) lasting minutes.
- New PR interval prolongation >280 msec.
- New prolongation of QTcF to >480 msec (absolute) or by ≥60 msec from baseline.
- New-onset atrial flutter or fibrillation, with controlled ventricular response rate: ie, rate <120 bpm.
- New-onset type I second-degree (Wenckebach) AV block of >30 seconds' duration.
- Frequent PVCs, triplets, or short intervals (<30 seconds) of consecutive ventricular complexes.

ECG Findings That May Qualify as Serious Adverse Events

- QTcF prolongation >500 msec.
- New ST-T changes suggestive of myocardial ischemia.
- New-onset left bundle branch block (QRS >120 msec).
- New-onset right bundle branch block (QRS >120 msec).
- Symptomatic bradycardia.
- Asystole:
 - In awake, symptom-free patients in sinus rhythm, with documented periods of asystole ≥3.0 seconds or any escape rate <40 bpm, or with an escape rhythm that is below the AV node;
 - In awake, symptom-free patients with atrial fibrillation and bradycardia with 1 or more pauses of at least 5 seconds or longer;
 - Atrial flutter or fibrillation, with rapid ventricular response rate: rapid = rate
 >120 bpm.
- Sustained supraventricular tachycardia (rate >120 bpm) ("sustained" = short duration with relevant symptoms or lasting >1 minute).

- Ventricular rhythms >30 seconds' duration, including idioventricular rhythm (HR <40 bpm), accelerated idioventricular rhythm (HR 40 bpm to <100 bpm), and monomorphic/polymorphic ventricular tachycardia (HR >100 bpm (such as torsades de pointes)).
- Type II second-degree (Mobitz II) AV block.
- Complete (third-degree) heart block.

ECG Findings That Qualify as Serious Adverse Events

- Change in pattern suggestive of new myocardial infarction.
- Sustained ventricular tachyarrhythmias (>30 seconds' duration).
- Second- or third-degree AV block requiring pacemaker placement.
- Asystolic pauses requiring pacemaker placement.
- Atrial flutter or fibrillation with rapid ventricular response requiring cardioversion.
- Ventricular fibrillation/flutter.
- At the discretion of the investigator, any arrhythmia classified as an adverse experience.

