6.6.4. Electrocardiograms

Changes from baseline for the ECG parameters QT interval, heart rate, QTcF interval, PR interval, and QRS interval will be summarized by treatment and time. For purposes of reporting study-level results, QTcF interval will be derived using Fridericia's heart rate correction formula applied to databased QT interval, and RR interval. The number (%) of participants with maximum increases from baseline will be tabulated by treatment as defined in Section 3.5.3. Numbers and percentages of participants meeting the categorical criteria will be provided and individual values listed in the study report. No formal inferential statistics will be applied to the ECG data.

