PCC	Potential Clinical Concern
PCSK9	Proprotein convertase subtilisin/kexin type 9
PD	Pharmacodynamic(s)
PGI-C	Patient Global Impression of Change
PGI-S	Patient Global Impression of Severity
PK	Pharmacokinetic(s)
PRO	Patient-reported outcome
PROMIS	Patient-Reported Measurement Outcome Information System
ProC3	N-terminal propeptide of type III procollagen
ProC6	C-terminal fragment of α3 chain of procollagen type VI
PBL	Percent change from baseline
PIIINP	Amino-terminal propeptide of type III procollagen

Abbreviation	Term
PR	Period of time from the onset of the P wave to the beginning of the
	QRS complex on an electrocardiogram
PT	Preferred term
QD	Quaque die (once-a-day)
QRS	Combination of Q-, R- and S- wave on an electrocardiogram
	representing ventricular depolarization
QTc	Corrected QT
QTcF	Corrected QT (Fridericia method)
RBC	Red blood cell
RC	Relatice change
RCBL	Relative change from baseline
RNA	Ribonucleic acid
ROW	Rest of World
RR	Respiratory rate
SAE	Serious adverse event
SAP	Statistical analysis plan
SD	Standard deviation
SE	Standard error
SI	Système international
SOP	Standard operating procedure
SPDFF	Segmental PDFF
T2DM	Type 2 diabetes mellitus
TEAE	Treatment Emergent Adverse Event
TDD	Total Daily Dose
TIMP-1	Tissue inhibitor of metalloproteinases 1
UA	Urinalysis
ULN	Upper limit of normal
ULQ	Upper limit of quantification
VCTE TM	Vibration-Controlled Transient Elastography
CCI	
VLDL	Very low-density lipoprotein
VRS	Verbal rating scale
WBC	White blood cell
WLPDFF	Whole Liver PDFF

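### The SAP's QTcF programming rule multiplies RR by 1000 where it must divide; followed as written, every derived QTcF is 100 times too small and all five prolongation categories are empty

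*SAP*

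**What the plan says.** SAP section 3.5.3 sets out ECG categories in Table 7, with a footnote that begins "QTcF -derived by programming as follows". The formula that goes with it is QT in msec divided by the cube root of the RR interval in seconds, "with RR (in sec) = RR (in msec) x 1000".

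The derived QTcF feeds two sets of rows in Table 7:

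- maximum post-dose value: ≤450, 450 to ≤480, 480 to ≤500, and >500 msec;
- maximum increase from baseline: ≤30, 30 to ≤60, and >60 msec.

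SAP section 6.6.4 says that "QTcF interval will be derived using Fridericia's heart rate correction formula applied to databased QT interval, and RR interval", and Protocol section 9.4.6.2 has the same sentence. The protocol adds that "Numbers and percentages of participants meeting the categorical criteria summarized in Table 5 will be provided"; the QTcF cells of that table use the same cut-points. Neither section gives a unit conversion. SAP Appendix 5 expands RR as "Respiratory rate".

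**The concern.** The footnote contradicts its own units. It asks for RR in seconds and then defines that quantity by multiplying milliseconds by 1000, so an RR of 800 msec would enter the formula as 800,000 seconds. This is the only computational instruction for QTcF in either document.

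The ECG is part of the safety assessment that both documents list among the secondary endpoints. If the rule is programmed literally, the error runs in the reassuring direction: each arm shows no QTcF prolongation whatever the ECGs contain, and the mean QTcF changes by arm and visit shrink 100-fold. A validator who reprograms from the SAP would reproduce the same wrong numbers.

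**Working it through.** **Inputs.** The formula and conversion are from SAP 3.5.3; the cut-points are from SAP Table 7. The documents give no ECG data, so the QT and RR values below are illustrative assumptions. The factor of 100 does not depend on them.

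**Step 1: the conversion.** One second is 1000 msec. As written, RR 800 msec becomes 800 × 1000 = 800,000 s. Correctly, it is 800 / 1000 = 0.8 s.

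**Step 2: the general error.** The ratio of the written divisor to the correct one is

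(RR × 1000)^(1/3) / (RR / 1000)^(1/3) = (10^6)^(1/3) = 100,

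whatever the RR. The QTcF as written is therefore exactly 1/100 of the Fridericia value.

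**Step 3: examples.**

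| QT (msec) | RR (msec) | Correct QTcF (msec) | Correct category | QTcF as written (msec) | Category as written |
|---|---|---|---|---|---|
| 400 | 800 | 400 / 0.8^(1/3) = 430.9 | ≤450 | 400 / 800,000^(1/3) = 4.31 | ≤450 |
| 460 | 800 | 460 / 0.8^(1/3) = 495.5 | 480 to ≤500 | 4.96 | ≤450 |
| 520 | 900 | 520 / 0.9^(1/3) = 538.6 | >500 | 520 / 900,000^(1/3) = 5.39 | ≤450 |

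A participant who moves from QT 400 to QT 460 at RR 800 has a true QTcF increase of 495.52 − 430.89 = 64.6 msec, which belongs in the >60 row. As written, the increase is 0.65 msec and falls in the ≤30 row.

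Over heart rates of 40 to 120 bpm and QT of 340 to 520 msec, the QTcF as written runs from 2.97 to 6.55 msec, against 297 to 655 msec when correctly derived.

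**Step 4: can any real ECG reach a prolongation row?** For the written value to exceed 450, QT would have to exceed 450 × (RR × 1000)^(1/3):

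- 35,717 msec at RR 500 (120 bpm);
- 41,774 msec at RR 800 (75 bpm);
- 45,000 msec at RR 1000 (60 bpm).

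For the written increase to pass 30 or 60 msec, the true increase would have to pass 30 × 100 = 3,000 or 60 × 100 = 6,000 msec. No ECG can do either. The three absolute and two increase categories that indicate prolongation are therefore empty in every arm, and so are the corresponding five cells of Protocol Table 5.

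**The case against.** The best reply is that this is an obvious slip with limited reach. The same line asks for RR in seconds, and Fridericia's correction is named in SAP Table 7, SAP 6.6.4 and Protocol 9.4.6.2, so a competent programmer would divide. If nobody did, values near 4 msec would stand beside uncorrected QT values near 400 msec in the by-visit summaries and listings, and would be caught.

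The outputs are also descriptive: both documents rule out formal inference on ECG data. At sites, a QTc judged against the protocol's ECG criteria comes from the machine or is "QTcF derived using sponsor-provided tool and reported QT and RR intervals". Findings such as "New prolongation of QTcF to >480 msec (absolute) or by ≥60 msec from baseline" can be reported as adverse events without this derivation. Uncorrected QT above 500 msec is still tabulated under Protocol Table 5.

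All of that stands, and it lowers the practical risk. It does not make the written rule right. Producing correct output would mean departing from the approved plan without a record of it, and a categorical table of zeros looks more plausible than a mean of 4 msec. The abbreviation entry for RR is a separate editorial slip and adds nothing to the size of the error.

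One caution: the layout of the footnote is disturbed in text extracted from the PDF, so the operator should be checked on the original page. The phrase itself is intact and reads as multiplication.

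**Conclusion.** The concern holds. The only written derivation of QTcF uses the wrong unit conversion and, followed as written, understates every QTcF and every QTcF change by a factor of exactly 100. All five QTcF prolongation categories would then be empty in every arm.

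This conclusion needs no assumption about the ECG data. It depends only on the rule being implemented literally, which is unlikely but is what the SAP instructs. The damage is confined to the programmed study-level QTcF outputs: the categories, the changes from baseline and the individual values. The uncorrected QT, heart rate, PR and QRS summaries, the site-level QTcF, the adverse event route and the primary endpoint are untouched. Because the rule is plainly wrong for a reported safety variable and correcting it requires no judgement, it should be fixed before the ECG outputs are programmed or, if they already exist, before they are relied on.

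**What to change.** - In SAP 3.5.3, change the conversion so that RR in seconds equals RR in msec divided by 1000, and make the same change in any programming specification that copies the line.
- In SAP Appendix 5, define RR as the ECG RR interval.
- Check the derived QTcF against the machine-reported value where that is recorded. Otherwise, hand-calculate a sample from the databased QT and RR.

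The cost is one character in the formula, one abbreviation entry and the matching line in any specification. No new data are needed and no clinical rule changes.

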Humans exposed to a drug who show no sign of liver injury (as determined by elevations in transaminases) are termed "tolerators," while those who show transient liver injury, but adapt are termed "adaptors." In some participants, transaminase elevations are a harbinger of a more serious potential outcome. These participants fail to adapt and therefore are "susceptible" to progressive and serious liver injury, commonly referred to as DILI. Participants who experience a transaminase elevation above 3 × ULN should be monitored more frequently to determine if they are an "adaptor" or are "susceptible."

In the majority of DILI cases, elevations in AST and/or ALT precede TBili elevations (>2 × ULN) by several days or weeks. The increase in TBili typically occurs while AST/ALT is/are still elevated above 3 × ULN (ie, AST/ALT and TBili values will be elevated within the same laboratory sample). In rare instances, by the time TBili elevations are detected, AST/ALT values might have decreased. This occurrence is still regarded as a potential DILI. Therefore, abnormal elevations in either AST OR ALT in addition to TBili that meet the criteria outlined below are considered potential DILI (assessed per Hy's law criteria) cases and should always be considered important medical events, even before all other possible causes of liver injury have been excluded.

The threshold of laboratory abnormalities for a potential DILI case depends on the participant's individual baseline values and underlying conditions. Participants who present with the following laboratory abnormalities should be evaluated further as potential DILI (Hy's law) cases to definitively determine the etiology of the abnormal laboratory values:

- Participants with AST/ALT and TBili baseline values within the normal range who subsequently present with AST OR ALT values >3 × ULN AND a TBili value
 >2 × ULN with no evidence of hemolysis and an alkaline phosphatase value
 <2 × ULN or not available.
- For participants with baseline AST OR ALT OR TBili values above the ULN, the
 following threshold values are used in the definition mentioned above, as needed,
 depending on which values are above the ULN at baseline:
 - Preexisting AST or ALT baseline values above the normal range: AST or ALT values >2 times the baseline values AND >3 × ULN; or >8 × ULN (whichever is smaller).

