 - Preexisting values of TBili above the normal range: TBili level increased from baseline value by an amount of at least 1 × ULN or if the value reaches >3 × ULN (whichever is smaller).

Rises in AST/ALT and TBili separated by more than a few weeks should be assessed individually based on clinical judgment; any case where uncertainty remains as to whether it represents a potential Hy's law case should be reviewed with the sponsor.

The participant should return to the investigator site and be evaluated as soon as possible, preferably within 48 hours from awareness of the abnormal results. This evaluation should include laboratory tests, detailed history, and physical assessment.

In addition to repeating measurements of AST and ALT and TBili for suspected cases of Hy's law, additional laboratory tests should include albumin, CK, direct and indirect bilirubin, GGT, PT/INR, total bile acids, and alkaline phosphatase. Consideration should also be given to drawing a separate tube of clotted blood and an anticoagulated tube of blood for further testing, as needed, for further contemporaneous analyses at the time of the recognized initial abnormalities to determine etiology. A detailed history, including relevant information, such as review of ethanol, acetaminophen/paracetamol (either by itself or as a coformulated product in prescription or over-the-counter medications), recreational drug, supplement (herbal) use and consumption, family history, sexual history, travel history, history of contact with a jaundiced person, surgery, blood transfusion, history of liver or allergic disease, and potential occupational exposure to chemicals, should be collected. Further testing for acute hepatitis A, B, C, D, and E infection and liver imaging (eg, biliary tract) and collection of serum samples for acetaminophen/paracetamol drug and/or protein adduct levels may be warranted.

All cases demonstrated on repeat testing as meeting the laboratory criteria of AST/ALT and TBili elevation defined above should be considered potential DILI (Hy's law) cases if no other reason for the LFT abnormalities has yet been found. Such potential DILI (Hy's law) cases are to be reported as SAEs, irrespective of availability of all the results of the investigations performed to determine etiology of the LFT abnormalities.

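### The SAP's potential DILI row counts AST/ALT-only elevations, but the protocol appendix it cites requires bilirubin as well, so the row is mislabelled

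*SAP*

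**What the plan says.** SAP Section 3.5.3, under its DILI and Hy's Law subheading, plans a table giving the number and percentage of participants per treatment group who meet the liver criteria, with different criteria for normal and abnormal baselines. For the definitions the reader is told to "see Appendix 6 of protocol for definition of potential Hy's Law and Potential DILI". Two row rules follow. The first is "Participants meeting the AST/ALT and TBili criteria will be categorized as potential Hy's Law cases". The second is that "participants who meet the AST/ALT criteria but not the TBili criteria will be categorized as potential DILI cases".

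Protocol Appendix 6 (Section 10.6) says that "abnormal elevations in either AST OR ALT in addition to TBili that meet the criteria outlined below are considered potential DILI". Its laboratory definition for a normal baseline covers participants who "subsequently present with AST OR ALT values >3 × ULN AND a TBili value" above 2 × ULN, with no evidence of hemolysis and with ALP below 2 × ULN or not available. For an abnormal baseline it changes the thresholds inside that same combined definition. For the enzymes the entry is "Preexisting AST or ALT baseline values above the normal range: AST or ALT values >2 times the baseline values AND >3 × ULN", or above 8 × ULN, whichever is smaller. A raised baseline TBili has its own threshold.

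The appendix closes with one rule for elevations that a second test confirms and that remain unexplained: those "meeting the laboratory criteria of AST/ALT and TBili elevation defined above should be considered potential DILI (Hy's law) cases". It adds that they "are to be reported as SAEs, irrespective of availability of all the results of the investigations performed". A transaminase rise above 3 × ULN on its own calls for more frequent monitoring. The appendix does not call it potential DILI.

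**The concern.** The SAP sends the programmer to Appendix 6 for two definitions, and the appendix contains one. The SAP then gives the appendix's term to the participants whom the appendix's TBili requirement leaves out.

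At stake is the meaning of a reported safety count. The clinical study report would show potential DILI by arm under a term the protocol defines, with nobody in that row meeting the definition. The same report will also summarize drug-induced liver injury as adjudicated (SAP Section 6.3.7.1), so similar terms would carry different meanings a few tables apart. The risk table in protocol Section 2.3 lists telling drug-induced injury from disease-related enzyme elevation as an issue for this study, which makes a clean label worth having.

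**Working it through.** The documents give no event rate or count on this point, so there is no figure to reproduce. The check compares the two definitions.

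**1. Side by side**

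| Profile | SAP 3.5.3 row | Protocol Appendix 6 |
|---|---|---|
| AST/ALT criterion met, TBili criterion not met | potential DILI | not a case |
| Both met, no hemolysis, ALP <2 × ULN or not available | potential Hy's Law | potential DILI (Hy's law) |
| Both met, but hemolysis or ALP ≥2 × ULN | potential Hy's Law, as the sentence is worded | not a case |

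**2. Enumeration at the normal-baseline thresholds.** Take peak AST/ALT of 2, 4 or 9 × ULN; TBili of 0.8, 1.5 or 2.5 × ULN; ALP of 1 or 2.5 × ULN; and hemolysis absent or present. That gives 3 × 3 × 2 × 2 = 36 profiles.

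- SAP potential DILI (enzymes >3, TBili ≤2): 2 × 2 × 2 × 2 = 16 profiles, of which 0 meet Appendix 6.
- SAP potential Hy's Law (enzymes >3, TBili >2): 2 × 1 × 2 × 2 = 8 profiles. Of these, 2 × 1 × 1 × 1 = 2 meet Appendix 6, and 6 fail on ALP or hemolysis.
- Neither row: 1 × 3 × 2 × 2 = 12 profiles.

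These are counts of profiles and say nothing about how often each occurs. They show that the SAP's potential DILI row and the protocol's category do not overlap.

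**3. Abnormal baseline.** For a baseline enzyme value of b × ULN, the Appendix 6 threshold is min(max(2b, 3), 8) × ULN. At b = 2 this is min(4, 8) = 4 × ULN. At b = 5 it is min(10, 8) = 8 × ULN. This changes who meets the enzyme criterion. TBili is still required, so the result in step 2 carries over.

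**4. Size.** Let X be the count in the Hy's Law row and Y the count in the AST/ALT-only row. The protocol-defined count is at most X. Read together, the two rows show X + Y, an excess of at least (X + Y) − X = Y.

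The documents give no value for Y. One participant in an arm of 50 is 1/50 = 2 percentage points, and less in an arm enlarged by participants first randomized to a QD regimen. As an illustration only, assume an AST/ALT-only rate q, with participants independent and n = 50. The expected count is 50q and the chance of at least one is 1 − (1 − q)^50.

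| Assumed q | Expected in row | Chance of at least one |
|---|---|---|
| 2% | 1 | 64% |
| 5% | 2.5 | 92% |
| 10% | 5 | 99.5% |

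**The case against.** The best defence is that a separate enzyme-only row is sensible. Appendix 6 itself says transaminase rises usually precede bilirubin rises and can herald a worse outcome. The SAP states the rule for each row, so a careful reader can see that the second row lacks bilirubin. Both documents also let the SAP modify the protocol's plans.

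The first two arguments stand: the row is worth keeping, and its content is open to view. The third fails here, because the SAP declares no departure and presents Appendix 6 as its source.

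Three stronger readings are tempting, and the documents do not support them.

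- *Entry enzymes up to 5 × ULN make such cases expected.* A reader might infer this from exclusion criterion 14. The SAP says its criteria differ by baseline, and under Appendix 6 a participant entering at 5 × ULN counts only above 8 × ULN. A high entry value alone puts nobody in the row.
- *The table creates a false hepatic signal.* A signal between arms would need an imbalance, which nothing in the documents predicts. Adjudicated DILI (SAP Section 6.3.7.1), eDish plots for each treatment group and separate ALT, AST and bilirubin flags (SAP Table 3) would also show enzyme-only elevations for what they are.
- *The table cannot be reconciled with the SAE data.* The SAE duty attaches to combined elevations, which fall in the Hy's Law row. That row is the one to compare with SAEs, bearing in mind that the duty also depends on repeat testing and on no other cause having been found.

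**Conclusion.** The mismatch is real and the point holds as one of labelling. SAP Section 3.5.3 attributes to Appendix 6 a category that the appendix does not contain. The potential DILI row holds only participants who fail the cited definition, and the protocol-defined cases are in the other row. The potential DILI row is thus misnamed rather than an inflated count of the right cases. Overstatement is certain only for the two rows taken together, and only when the AST/ALT-only count is above zero.

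The size cannot be derived from the documents, and the rates tabulated above are assumptions. The conclusion assumes that the TBili criterion is judged over each participant's whole follow-up, since the SAP sets no requirement that the two elevations coincide. The table is descriptive, and neither the primary analysis nor any other efficacy result depends on it. This is a minor correction, worth making because it changes what a reported safety count means.

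**What to change.** Reconcile SAP Section 3.5.3 with protocol Appendix 6:

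- Relabel the second row as AST/ALT criterion met without TBili criterion.
- Report one potential DILI (Hy's law) row on the full Appendix 6 laboratory definition: the AST/ALT and TBili thresholds for normal and abnormal baselines, no evidence of hemolysis, and ALP below 2 × ULN or not available.
- Footnote that this is a laboratory screen, and that confirmation on repeat testing and exclusion of other causes are not part of the count.

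If the sponsor prefers to keep the present label, the SAP should say that the row is its own category and departs from Appendix 6. The cost is a few lines of SAP text and a table label, plus programming of the ALP and hemolysis conditions if these are not already in place. No new data collection is needed for the relabelling, and both rows are kept.
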